# 7.3. Clinical Study Rationale

MS is a serious, life-threatening and disabling disease that is prevalent in young and middle-aged adults. The progressively debilitating nature of the disease has an enormous impact, not only on the quality of life of the patient, but also on their families, health systems and the national economy. New drugs are needed to positively impact the lives of patients and reduce the healthcare cost burden associated with relapses.

Clinical experience with fingolimod (recently approved for the treatment of RMS) strongly supports the rationale for therapeutically targeting S1P1R in MS. Fingolimod is an agonist of four of the five S1P receptors: S1P1R, S1P3R, S1P4R, and S1P5R (Mandala, 2002; Brinkmann, 2002). Fingolimod induces lymphocyte sequestration in peripheral lymphoid organs, resulting in lymphopenia in several animal species and in humans; this response represents a clearly defined PD effect of S1P1R stimulation and a likely mechanism of fingolimod's clinical efficacy (Kappos, 2006; Sanna, 2006). In a head-to-head clinical study, fingolimod displayed superior efficacy compared to IFN  $\beta$ -1a (Cohen, 2010). Thus, fingolimod has provided clinical evidence for the effectiveness of a drug that targets S1P1R.

There are a number of AEs associated with fingolimod treatment that may limit its use in the RMS population. Cardiac AEs such as bradycardia and other heart conduction abnormalities have been observed with fingolimod in the clinical development program and in the postmarketing setting, which increased the need for more intensive cardiac monitoring for RMS patients when receiving the first dose of fingolimod. Elevations in liver enzymes (3 times the upper limit of normal [ULN]) have also been observed in the range of 8-12%, consistent with liver pathology (Cohen, 2010; Kappos, 2006). These toxicities may be a consequence of the drug lacking specificity for S1P1R, from having higher than necessary exposures, or from having pharmaceutic liabilities related to fingolimod's structural class. Additionally, due to complex absorption, distribution, metabolism and excretion properties including an extremely long half-life (89 to 157 hours), the PD effects of fingolimod are prolonged, with patients requiring several weeks before the number of circulating lymphocytes return to normal following cessation of treatment (Kovarik, 2004; Budde, 2002). This may have clinical safety consequences, particularly if patients develop infections or other treatment-related complications.

All of the currently approved drugs have therapeutic, safety and/or logistical limitations. All but fingolimod are administered by injection, presenting challenges associated with injection-related AEs, compliance and convenience. First-line therapies have modest efficacy coupled with side effect profiles that affect patient quality of life and adherence to therapy. Second- and third-line therapies have better efficacy profiles but significant safety issues. There is a pressing need for an MS treatment that is highly effective, well tolerated, and orally active.

A clinical development program for RPC1063 is being pursued in MS because: (i) it is a potent and selective orally bioavailable S1P1R agonist, (ii) it has a short half-life allowing for rapid clearance of the drug in the setting of potential treatment related complications, (iii) it may allow for a more rapid recovery of lymphocytes into the normal range in RMS patients, and (iv) RPC1063 may have an improved safety and tolerability profile over existing RMS therapies including other S1PR agonists.

The objective of the RPC1063 clinical development program in RMS is to demonstrate that RPC1063 administered orally as monotherapy is safe and effective in reducing the frequency of clinical exacerbations and in delaying the accumulation of physical disability exacerbations in RMS patients.

This Phase 2/3 clinical trial consisting of a placebo-controlled (Part A, Phase 2) and active comparator trial (Part B, Phase 3) versus IFN  $\beta$ -1a is the first pivotal study of the RPC1063 clinical development program. Part A is a randomized, double-blind comparison of RPC1063 to a placebo control in patients with RMS to characterize the short-term efficacy and safety of RMS in improving disease activity as measured by MRI parameters. Part B characterizes the efficacy and safety profile of RPC1063 on longer-term clinical outcomes (e.g., relapse rate and disability progression) in RMS patients.

Both of these parts will provide substantial data characterizing the clinical effects of RPC1063 in RMS patients. An active comparator design was chosen based on the significant challenges in conducting long-term placebo-controlled studies in which patients are at increased risk for experiencing irreversible disability progression from placebo treatment. IFN  $\beta$ -1a was chosen based upon its wide use in many global regions as a standard of care therapy, its acceptability as a reference comparator based on other trials in RMS over the last 5 years, and its relative lower frequency of administration (weekly) compared to other therapies.

#### 8. STUDY OBJECTIVES AND ENDPOINTS

# 8.1. Study Objectives

# 8.1.1. Primary Study Objectives

#### Part A

To demonstrate the superior efficacy of RPC1063 compared to placebo by showing a reduction in the cumulative number of total gadolinium enhancing (GdE) lesions from Week 12 to Week 24 in patients with RMS.

#### Part B

To assess whether the clinical efficacy of RPC1063 is superior to IFN  $\beta$ -1a reducing the rate of clinical relapses at the end of Month 24 in patients with RMS.

# 8.1.2. Secondary Study Objectives

#### Part A

- To assess the proportion of patients who are free of GdE lesions at Week 24
- To assess the effect of RPC1063 on the cumulative number of new/enlarging T2 lesions from Week 12 to Week 24
- To compare the clinical efficacy of RPC1063 to placebo in patients with RMS as assessed by reduction in annualized relapse rate (ARR) and proportion of relapse free patients at Week 24
- To assess the safety and tolerability of RPC1063 in patients with RMS
- To assess the pharmacokinetics (PK) and PD of RPC1063 in patients with RMS

#### Part B

- To assess the effect of RPC1063 on the proportion of patients with new/enlarging T2 lesions at Month 24
- To evaluate whether the efficacy of RPC1063 is superior to IFN β-1a in delaying the accumulation of disability, as assessed by the Multiple Sclerosis Functional Composite (MSFC), and visual function as measured by the low contrast visual acuity test (LCLA) (Balcer, 2000).
- To evaluate whether the efficacy of RPC1063 is superior to IFN β-1a in delaying the accumulation of disability, as assessed by the Expanded Disability Status Scale (EDSS)
- To assess the effect of RPC1063 on brain atrophy over 24 months
- To evaluate the effect of RPC1063 on patient-reported quality of life as assessed by the Multiple Sclerosis Quality of Life-54 (MSQOL-54)
- To assess the safety and tolerability of RPC1063 in patients with RMS

# 8.1.3. Exploratory Study Objectives

#### Part A

## Part B

# 8.2. Endpoints

## 8.2.1. Efficacy Endpoints

#### Part A

Primary Efficacy Endpoint:

• Total number of GdE lesions, assessed on brain MRIs from Week 12 to Week 24

Key Secondary Efficacy Endpoints (rank ordered):

- The number of GdE lesions at Week 24
- Total number of new or enlarging hyperintense T2-weighted brain MRI lesions from Week 12 to Week 24
- ARR at the end of Week 24

## **Exploratory Endpoints:**

#### Part B

# Primary Efficacy Endpoint:

• ARR at the end of Month 24

## Key Secondary Efficacy Endpoints (rank ordered):

- The number of new or enlarging hyperintense T2-weighted brain MRI lesions over 24 months
- The number of GdE brain MRI lesions at 24 months
- Time to onset of disability progression as defined by a sustained worsening in EDSS of 1.0 points or more, confirmed after 3 months and after 6 months

#### Other Secondary Efficacy Endpoints

- Proportion of patients who are GdE lesion-free at Month 24
- Proportion of patients who are new or enlarging T2 lesion-free at Month 24
- The percent change in normalized brain volume (atrophy) on brain MRI scans from baseline to 24 months
- Change in MSFC score from Baseline to Month 24 (including the Low-Contrast Letter Acuity Test [LCLA] measurement of visual function as a component)
- Change in MSQOL-54 score from Baseline to 24 months

#### **Exploratory Endpoints:**

## 8.2.2. Safety (Secondary) Endpoints

#### Part A

Cardiac safety and tolerability during initial dose titration will be evaluated in Part A patients according to the following monitoring schedule:

- Day 1 (all Part A patients): Observation of patients predose and for the first 6 hours following initial dose administration; ECG predose and at Hour 6; continuous Holter monitoring for 15 minutes predose and for 24 hours following dose administration.
- Day 5 (first 75 patients): Observation of patients predose and for the first 6 hours following dose administration; ECG predose and at Hour 6; continuous Holter monitoring for 15 minutes predose and for 24 hours following dose administration.

• Day 8 (first 75 patients): Continuous Holter monitoring for 15 minutes predose and for 24 hours following dose administration.

If clinically significant heart rate reduction or cardiac conduction abnormalities are not observed in the first 75 patients that are treated, Day 5 and Day 8 monitoring will be discontinued for the remaining patients enrolled in the study.

#### Part B

Monitoring during initial dosing for Part B will include:

Day 1 (all Part B patients): Observation of patients predose and for the first 6 hours following initial dose administration; ECG predose and at Hour 6

Monitoring during initial dosing for Part B may be modified based on safety and tolerability results observed during Part A, and will be implemented as needed in an amendment to this clinical study protocol.

## Part A and Part B

Safety and tolerability will be evaluated in this study by the incidence and type of AEs, SAEs, AEs leading to discontinuation of study treatment, the incidence and type of laboratory abnormalities, vital sign, ECG, and physical exam abnormalities in all patients. In addition, descriptive characterization of target AEs of interest including bradycardia and heart conduction abnormalities (ECG, vital signs, continuous Holter monitoring [Part A only]), pulmonary toxicity (FEV1, FVC measurements), and lung diffusion capacity testing [DLCO] measurements), macular edema (optical coherence tomography [OCT]), hepatotoxicity (LFTs), cutaneous malignancy (dermatological exams), and suicidality (Columbia- Suicide Severity Rating Scale [C-SSRS]) will occur in both Part A and Part B of the study.

Safety assessments will include the following:

- AEs
- Laboratory evaluations
- Vital sign measurements
- ECG results
- Continuous Holter monitoring
- Physical and neurological examination
- OCT
- Pulmonary function tests
- Dermatological examination
- Columbia-Suicide Severity Rating Scale (C-SSRS)

#### 8.2.3. PK and PD Endpoints

PK and PD assessments will include the following:

- Standard PK sampling to determine plasma concentration of RPC1063 and active metabolites
- CBC with differential (differential will be blinded)
- Plasma protein biomarker analysis (e.g., cytokines, chemokines, other inflammatory proteins)
- Total immunoglobulins (Igs) IgA, IgG, IgM

PK data from this study may be integrated with PK data from other clinical trials to further enhance a population PK analysis. Results from any population PK analysis will be documented in a separate pharmacometric report.

## 9. INVESTIGATIONAL PLAN

# 9.1. Overall Study Design and Plan

Study RPC01-201 is a multi-center, randomized, double-blind, placebo-controlled (Part A) and double-blind, double-dummy, active-controlled (Part B) parallel group study to evaluate the efficacy and safety of RPC1063 administered orally to patients with RMS.

In Part A of the study, two doses of RPC1063 will be administered daily for 24 weeks with an efficacy and safety comparison to a placebo control. This will be followed by Part B of the study, where two doses of RPC1063 will be administered daily for a 24 month period compared to an active control, IFN  $\beta$ -1a.

An interim analysis of Part A will be completed approximately 1 month prior to completion of Part A enrollment. Part B will commence after a DMC reviews the interim analysis data and performs a thorough safety review. Patients dosed in Part A will be ineligible for participation in Part B.

It is anticipated that the study will be performed at approximately 100-125 sites for Part A and for Part B in North America and Europe.

The study designs for Part A and Part B are shown in Figure 1.

Tests and assessments are outlined in Table 1 and Table 2 (Part A), Table 3 and Table 4 (Part B), and Table 5 (cardiac monitoring during dose titration), additional details regarding procedures are included in Section 10. Assessments are described in Section 11.

## Part A

Part A is a randomized, double-blind comparison of RPC1063 to a placebo control in patients with RMS, per revised 2010 McDonald criteria (McDonald, 2010; Polman, 2011). Approximately 210 patients who meet eligibility criteria as assessed during the 30-day screening period will be randomly assigned 1:1:1 to receive one of the three following regimens, up to Week 24:

- Placebo oral capsule daily
- 0.5 mg RPC1063 oral capsule daily
- 1 mg RPC1063 oral capsule daily

The randomization will be stratified by country.

Brain MRI scans will be performed at Week 0, Week 8, and every 4 weeks thereafter, up to Week 24. Patients will be evaluated for relapses throughout the study.

Patients who complete the 24 weeks placebo-controlled treatment period will have the option of entering a blinded extension period. During the blinded extension period, the sponsor and CRO will be blinded until the Week 24 primary endpoint is reached by all patients and the data through Week 24 are final, after which the sponsor and CRO will be unblinded to treatment assignment. Investigators and patients will remain blinded throughout the blinded extension period. Patients assigned to either RPC1063 treatment group during the double-

blind placebo-controlled period will continue in their respective treatment groups during the blinded extension; patients assigned to the placebo treatment group will be randomly assigned in a 1:1 fashion to one of the two RPC1063 treatment groups for the blinded extension. The blinded extension study will continue until all patients who choose to participate have received at least 48 weeks of treatment (total of at least 72 weeks for Part A, 24 weeks in placebo-controlled period and at least 48 weeks additional weeks in the blinded extension). For patients continuing to the blinded extension, MRI scans will be performed 24 and 48 weeks after Week 24 (at approximately Weeks 48 and 72 and annually after Week 72) or at End of Study visit. All patients who successfully complete the blinded extension period will be offered the opportunity to enter a long-term extension period, which will be the subject of a separate protocol.

A "dual assessor" approach will be used to evaluate efficacy and safety to prevent potential unblinding as result of observed efficacy, AEs, or laboratory changes. Separate treating and examining investigators will be designated at each center prior to randomization (refer to Section 9.1.2.1 for additional details). Patients will be instructed to not disclose symptoms related to their treatment regimen to the blinded evaluator (examining investigator). The blinded evaluator should communicate with patients only as needed to complete the neurologic examinations.

The MSQOL-54 will also be assessed during Part A.

An analysis center with no knowledge of a patient's treatment or outcomes will perform MRI evaluations.

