#### 9.5. Treatment

#### 9.5.1. Treatments Administered

The Investigator must ensure that the investigational product will be used only in accordance with the protocol.

Part A of the study is randomized and double-blinded with regard to treatment with RPC1063 and matching placebo in order to prevent bias in treatment allocation and in the assessment of effect. The Investigator site personnel, as well as the Sponsor and their representatives involved in the monitoring or conducting the study, and the patients will all be blinded to the study drug codes.

Part B of the study is randomized and double-blind, double-dummy with regards to treatment with RPC1063 or IFN  $\beta$ -1a and their corresponding matching placebo in order to prevent bias in treatment allocation and in the assessment of effect. The prolonged treatment period (24 months) will provide additional safety and efficacy data; information that is relevant to RMS, a chronic, highly variable, slowly progressing disease.

In both Part A and Part B of the study, a "dual assessor" approach will be used to evaluate efficacy and safety to prevent potential unblinding as result of observed efficacy, AEs, or laboratory changes

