#### Part A

Part A is a randomized, double-blind, placebo-controlled study with limited access to the randomization code. RPC1063 and placebo capsules will be identical in physical appearance. The treatment each patient will receive will not be disclosed to the Investigator, Evaluator, study center personnel, patient, Sponsor and their representatives. The treatment codes will be held according to an IVRS. Further instructions will be provided in a separate IVRS manual.

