#### 9.5.11. Unblinding Procedures for Individual Patients

A patient's treatment group assignment blind will not be broken until the end of the study unless medical treatment of that patient depends upon knowing whether the patient is receiving active drug. In the event that the blind needs to be broken because of a medical emergency, the investigator may unblind an individual patient's treatment allocation. The investigator should attempt to contact the Medical Monitor as soon as practicable to discuss the medical emergency and the reason unblinding. The treatment assignment will be unblinded through an IVRS. Reasons for treatment unblinding must be clearly explained and justified in the eCRF. The date on which the code was broken together with the identity of the person responsible must also be documented.

A PK sample will be obtained whenever possible for patients with any AE resulting in unblinding, discontinuation or SAE.

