## **14.1.** Routine Monitoring

Sponsor assigned monitors will conduct regular site visits to the investigational facilities for the purpose of monitoring various aspects of the study. The Investigator must agree to Sponsor-authorized personnel having direct access to the clinical (or associated) files and clinical study supplies (dispensing and storage areas) for all study patients considered for study entry for the purpose of verifying entries made in the eCRF, and assist with their activities, if requested. The Investigator will make available adequate time and space for monitoring visits.

The site must complete the eCRFs in a timely manner and on an ongoing basis to allow regular review by the Study Monitor.

Whenever a patient name is revealed on a document that is to be collected for the Sponsor the name must be blacked out permanently by the site personnel, leaving the initials visible, and annotated with the patient number as identification.

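### Protocol Section 9.1 unblinds the sponsor and CRO, with no limit by role, while the Part A blinded extension is still running, in conflict with Sections 9.5.1, 9.5.4 and 9.5.11

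*Protocol*

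**What the plan says.** Protocol Section 9.1 (Part A) sets a specific rule for the extension. The sponsor and CRO stay blinded until every patient has reached Week 24 and the results to that point have been finalised. The rule then continues: "after which the sponsor and CRO will be unblinded to treatment assignment. Investigators and patients will remain blinded throughout the blinded extension period". It gives no list of roles, no access restriction and no separation between staff who analyse data and staff who deal with sites.

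Three other places in the protocol speak to the same matter, and none mentions this planned unblinding:

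- Section 9.5.1, on Part A, names the investigator's staff and then goes on: "as well as the Sponsor and their representatives involved in the monitoring or conducting the study, and the patients will all be blinded". What is withheld from them is the treatment code.
- Section 9.5.4, Part A, says: "The treatment each patient will receive will not be disclosed to the Investigator, Evaluator, study center personnel, patient, Sponsor and their representatives".
- Section 9.5.11 says: "A patient's treatment group assignment blind will not be broken until the end of the study". The only exception given is medical need in that patient.

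On who is in contact with sites, Section 14.1 says: "Sponsor assigned monitors will conduct regular site visits to the investigational facilities for the purpose of monitoring various aspects of the study". Section 14 describes these people as the sponsor's monitors or representatives and has them check eCRF data against source.

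**The concern.** Taken at its word, the rule in Section 9.1 gives each patient's dose to everyone at the sponsor and the CRO while patients are still being dosed and assessed under blind. That group includes people who talk to investigators, verify source records and take part in decisions about individual patients:

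- Section 9.4.4.1 provides for stopping study medication for non-compliance after consultation that includes the Medical Monitor or Study Monitor and, when appropriate, the sponsor.
- Section 16.3 makes continuation after a significant deviation a joint decision, documented by the investigator, the sponsor and the Medical Monitor.
- Section 9.5.9 (Part A) has persistent non-compliance discussed with the Medical Monitor to decide on withdrawal.

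Relapse determination, adverse event causality and discontinuation involve judgment. The protocol takes care to shield raters from anything that could reveal treatment, and people in contact with sites who know the dose weaken that protection. What is at stake is the randomised long-term comparison of 0.5 mg with 1 mg. There is also a practical difficulty: staff cannot comply with all four passages as they stand.

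**Working it through.** **Do the passages conflict?**

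1. Section 9.1 covers the sponsor and CRO without restriction. The site-visiting monitors belong to the sponsor side (Sections 14 and 14.1), so they are covered although not named. SAP Section 1 also says clinical monitoring is contracted out, but that SAP covers Part B only.
2. Sections 9.5.1 and 9.5.4 apply to Part A and set no end date. The extension belongs to Part A: its dosing is described within Section 9.5.1, and Section 11.2.1 (monitoring of AEs and SAEs) treats Part A as having two periods.
3. Section 9.5.11 ties the blind to the end of the study, not to Week 24.
4. No passage limits the sponsor's blinding to the placebo-controlled weeks except Section 9.1 itself. The conflict is in the current text.

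**How much of the extension is exposed?**

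The plan's own figure reproduces: 24 + 48 = 72 weeks minimum for a patient who enters the extension (Section 9.1).

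Accrual length E is not stated, but Section 13.6.7 implies it. The interim falls about 1 month (30.4375/7 = 4.35 weeks) before enrolment ends, with about 45% of patients having completed 12 weeks and 80–90% treated. Under uniform accrual:

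- From the 45%: (E − 4.35 − 12)/E = 0.45, so E = 16.35/0.55 = 29.7 weeks.
- Check: (29.7 − 4.35)/29.7 = 85% treated at the interim, inside the stated 80–90%.
- The 80–90% range alone gives E = 4.35/0.20 = 21.7 to 4.35/0.10 = 43.5 weeks.

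Let L be the lag in weeks from the last patient's Week 24 to final data. The documents do not give it, so it is shown as a range. A patient who enters u weeks after the first patient starts the extension at u + 24. Unblinding comes at E + 24 + L, and the common end is E + 72. Then:

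- Exposed time per patient who stays = (E + 72) − (E + 24 + L) = 48 − L, whatever u is.
- Mean extension time = 48 + E/2.
- Exposed share of extension patient-time = (48 − L)/(48 + E/2).

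| L (weeks) | E = 22 | E = 29.7 | E = 43.5 |
|---|---|---|---|
| 0 | 81% | 76% | 69% |
| 4 | 75% | 70% | 63% |
| 8 | 68% | 64% | 57% |
| 12 | 61% | 57% | 52% |
| 16 | 54% | 51% | 46% |
| 20 | 47% | 45% | 40% |

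The share reaches one half at L = 24 − E/4, which is 18.5, 16.6 and 13.1 weeks for the three accrual lengths.

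Sensitivity at E = 29.7 and L = 8: 10% dropout per 48 weeks gives 62%. Running 26 weeks past Week 72, which Table 2 footnote 3 allows, gives (40 + 26)/(62.9 + 26) = 74%. Measured by calendar time from the first extension entry, the share is (48 − L)/(48 + E): 62% at L = 0, and below half once L exceeds about 9 weeks.

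By enrolment order, again at E = 29.7 and L = 8, the first and last enrolled patients each have 40 exposed weeks. As a share of their own extension this is 40/77.7 = 51% and 40/48 = 83%.

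**The case against.** The best reply is that Section 9.1 is the specific rule and the others are general. Sections 9.5.1 and 9.5.4 describe a placebo-controlled comparison, and the extension has no placebo arm. Section 9.5.11 is headed as a procedure for individual patients and is mainly about emergency code breaks. This is a coherent reading, and it is why the conflict with Section 9.5.11 is claimed only on its literal words. But no passage states that limit, and Sections 9.5.1 and 9.5.4 carry no exception, so the reconciliation is still needed.

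The second reply is that the route to bias is indirect, and much of this stands. The treating investigator decides on relapse from scores taken by the blinded evaluator and assigns AE causality, and investigators stay blinded. MRI is read centrally by people with no knowledge of treatment (Sections 9.1 and 9.1.2.2). The Medical Monitor is mostly consulted, not given the decision, and is covered by Section 9.1 only if employed by the sponsor or CRO, which is an assumption.

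Third, no visible confirmatory result is touched. The Part A primary and key secondary endpoints end at Week 24, and those data are final before unblinding. The Part A SAP is a separate document not available here, so the intended use of the extension comparison and any access controls described there cannot be judged.

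**Conclusion.** The conflict is real and should be resolved. It concerns only the long-term 0.5 mg versus 1 mg extension data. The size of any bias cannot be computed from the documents. On the assumptions of uniform accrual over about 30 weeks and a lag of 0 to 12 weeks, about 57% to 76% of extension patient-time follows the unblinding. Above a lag of about 13 to 18 weeks, depending on accrual, the share falls below half.

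A reader might infer more than this, and four such inferences are not supported:

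- That at least 48 of 72 weeks are affected. The 48 weeks are the whole minimum extension. The exposed part is 48 weeks minus the lag, plus any overrun.
- That most of the extension is exposed as a matter of fact. This depends on an undocumented lag.
- That late enrollees are exposed longest. Absolute exposed time is about the same for everyone who stays; only the share is larger for late enrollees.
- That the extension could not be reported as double-blind. The synopsis reserves that label for the 24-week period and calls the extension blinded. The supportable statement is that a report could not claim the sponsor-side blinding promised in Sections 9.5.1, 9.5.4 and 9.5.11.

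**What to change.** Reword Section 9.1 (Part A) so that, once the Week 24 data are final, patient-level assignments go only to a listed group of sponsor and CRO staff who analyse and report Week 24 and have no contact with sites. State that clinical monitors, the Medical Monitor and other site-facing staff remain blinded until the extension database is locked. Cross-refer this exception in Sections 9.5.1, 9.5.4 (Part A) and 9.5.11 so that the four passages agree.

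The cost is protocol wording and an access list in the randomisation system, with no new roles. The Week 24 analysis and report can proceed as planned. The small downside is that some sponsor and CRO staff wait until the extension lock for patient-level assignments.
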